- For GH treatment naïve participants: Impaired height defined as at least 2.0 standard deviation below the mean height for chronological age and sex at screening according to the standards of Centers for Disease Control and Prevention.²
- For GH treatment naïve participants: Confirmed diagnosis of TS by 30-cell (or more) lymphocyte chromosomal analysis *or* confirmation of TS and TS mosaicism using CGH-array.

Applicable to children with NS:

- Diagnosis of NS according to local clinical practice.
- Age:

- Male participants: Age equal to or above 11.0 years and below 18.0 years at screening.
- Female participants: Age equal to or above 10.0 years and below 18.0 years at screening.
- Open epiphyses; defined as bone age < 14 years for females and bone age < 16 years for males.
- For GH treatment naïve participants: Clinical diagnosis of NS according to van der Burgt score list and genetic test result³ OR confirmed mutation in any of the genes associated with NS before allocation.

Applicable to children with ISS:

- Age:
 - Male participants: Age equal to or above 11.0 years and below 18.0 years at screening.
 - Female participants: Age equal to or above 10.0 years and below 18.0 years at screening.
- Open epiphyses; defined as bone age < 14 years for females and bone age < 16 years for males.
- For GH treatment naïve participants: Impaired height defined as at least 2.5 standard deviations below the mean height for chronological age and sex at screening
- For GH treatment naïve participants: Normal GH secretion (GH peak above 7 ng/mL) during GH stimulation test performed within 18 months prior to screening.
For Korea: Please see local requirements in Appendix 11 (Section [10.11](#))
- For GH treatment naïve participants: Bone age not delayed more than 2 years compared to chronological age at screening.

Key exclusion criteria:

- Children with suspected or confirmed growth hormone deficiency according to local practice.
- Children diagnosed with diabetes mellitus or screening values from the central laboratory of
- Fasting plasma glucose above or equal to 126 mg/dL (7.0 mmol/L) or
- HbA_{1c} above or equal to 6.5%.
- Current inflammatory diseases requiring systemic corticosteroid treatment for longer than 2 consecutive weeks within the last 3 months prior to screening.

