2.3.1 Risk assessment

Table 2-1 Risk assessment

Potential risk of clinical significance	Summary of data/rationale for risk	Mitigation and monitoring strategy
Study interventions (somapacitan)		
Allergic reaction	Allergic hypersensitivity may occur with the administration of somapacitan. Acute generalised hypersensitivity reactions are generally known to occur within the first few hours after the injection and may include headache, nausea, vomiting, dizziness, sweating, flushing, change in blood pressure and difficulties in breathing.	Patients with known or suspected hypersensitivity to study product, any constituents of the product or related products will not be enrolled in the study (see exclusion criteria in Section 5.2). Signs of allergic hypersensitivity will be monitored closely throughout the study. The first dose of somapacitan will be administered at the study site, and the participants are therefore monitored very closely after first dosing. Allergic type hypersensitivity should be treated as per local practice at the investigator's discretion.
Diabetes mellitus	Treatment with GH may decrease insulin sensitivity, particularly at higher doses in susceptible patients. Consequently, hyperglycaemia may occur in participants with inadequate insulin secretory capacity.	Glucose levels should be monitored periodically in all patients treated with GH, especially in those with risk factors for diabetes mellitus, such as obesity, or a family history of diabetes mellitus. Patients with pre-existing type 1 or type 2 diabetes mellitus or impaired glucose tolerance are excluded from participation in the study. The doses of anti-hyperglycaemic medicinal products may require adjustment when GH therapy is instituted in these patients.

Potential risk of clinical significance	Summary of data/rationale for risk	Mitigation and monitoring strategy
Intracranial hypertension	Patients with intracranial hypertension are at increased risk of worsening of the condition by treatment with GH, because a major adverse effect of GH treatment is fluid retention.	In the event of severe or recurrent headache, visual symptoms, nausea, and/or vomiting, a fundoscopic examination for papilloedema is recommended. If papilloedema is confirmed, a diagnosis of benign intracranial hypertension should be considered and if appropriate the GH treatment should be discontinued. If GH treatment is restarted, careful monitoring for symptoms of intracranial hypertension is necessary.

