2.3.3 Overall benefit-risk conclusion

Overall, the safety profile of somapacitan is similar to the well-known safety profile of daily growth hormone products e.g., Norditropin® and no new safety concerns have been found during the conduct of the somapacitan study program.

There are well known risks associated with administration of injectable medication³⁶ as well as procedural risks as described in [Table 2-1](#). In this study the risks associated with administration of trial product as well as the risks associated with the study procedures are expected to be comparable to what is seen in routine clinical practice.

More detailed information about the known and expected benefits and risks and reasonably expected adverse events (AE) of somapacitan may be found in the IB.

Taking into account the measures taken to minimise risk and burden to children participating in this study, the potential risks identified in association with somapacitan are justified by the anticipated benefits that may be afforded to children with SGA, TS, NS and ISS.

3 Objectives, endpoints and estimands

Table 3-1 Objectives and endpoints

Objectives	Endpoints		
Primary	Title	Time frame	Unit

 To evaluate the safety of once-weekly somapacitan in children, either naïve or non-naïve to GH treatment, within each of the four indications: SGA, TS, NS or ISS. 		Primary endpoint: Number of adverse events (AEs) From baseline (week 0) to week 26 Number of AEs	
		Secondary supportive safety endpoint: Number of adverse events (AEs) possibly or probably related to somapacitan From baseline (week 0) to week 26 Number of AEs	
Secondary	Title	Time frame	Unit

 To evaluate the long-term safety of once-weekly somapacitan in children, either naïve or non-naïve to GH treatment, within each of the four indications: SGA, TS, NS or ISS. 		Secondary supportive safety endpoint: Number of adverse events (AEs) From baseline (week 0) to week 156 Number of AEs	

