4.4 End of study definition

The end of the study is defined as the date of the last participant's last visit in the sub-study to finish last.

For all participants in the study

A participant is considered to have completed the study if he/she has completed all periods of the main and extension period I of the study including visit 18.

The primary endpoint is evaluated from visit 2 to visit 7 for each indication/sub-study. The primary completion date (PCD) is defined as the date of visit 7 (week 26) on which the last participant in the first indication to complete the main period has an assessment for the primary endpoint. If the last participant is withdrawn early, the PCD is considered the date when the last participant in the first indication to complete the main period would have completed visit 7.

For participants continuing in extension period II

Participation in this extension period II will be offered to continue treatment with somapacitan until somapacitan becomes available for prescription for treatment of SGA, TS, NS or ISS or until October 2027 at the latest. Therefore, there is no predefined specific period that must be completed.

5 Study population

Prospective approval of protocol deviations to recruitment and enrolment criteria, also known as protocol waivers or exemptions, is not permitted.

Pre-screening is defined as review of the patient medical records, including handing out participant information, as well as database review. Any pre-screening activities must be documented on site by the investigator.

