5.2 Exclusion criteria

Participants are excluded from the study if any of the following criteria apply:

1. Known or suspected hypersensitivity to study intervention(s) or related products.
2. Previous allocation into same sub-study in this study.
3. Receipt of any investigational medicinal product within 3 months before screening or participation in another clinical study at the time of allocation.
4. Children with suspected or confirmed growth hormone deficiency according to local practice.
5. Children diagnosed with diabetes mellitus or screening values from the central laboratory of
 - a. fasting plasma glucose above or equal to 126 mg/dL (7.0 mmol/L) or
 - b. HbA_{1c} above or equal to 6.5%.
6. Current inflammatory diseases requiring systemic corticosteroid treatment for longer than 2 consecutive weeks within the last 3 months prior to screening.
7. Children requiring inhaled glucocorticoid therapy at a dose greater than 400 µg/day of inhaled budesonide or equivalent (i.e., 250 µg/day for fluticasone propionate) for longer than 4 consecutive weeks within the last 12 months prior to screening.
8. History or known presence of any malignancy, intracranial tumour, or intracranial cyst.
9. History or known presence of active Hepatitis B or Hepatitis C (exceptions to this exclusion criterion is the presence of antibodies due to vaccination against Hepatitis B).

10. Any disorder, which in the investigator's opinion, might jeopardise participant's safety or compliance with the protocol.
11. The participant or the parent/legally acceptable representative is likely to be non-compliant in respect to study conduct, as judged by the investigator.
12. Female who is pregnant, breast-feeding or intends to become pregnant or is of childbearing potential and not using adequate contraceptive method, as defined in Appendix 4 (Section [10.4](#)).
13. Male of reproductive age who, or whose female partner(s), is not using an adequate contraceptive method, as defined in Appendix 4 (Section [10.4](#)).

Applicable to children with SGA:

14. Any known or suspected clinically significant abnormality likely to affect growth or the ability to evaluate growth with height, such as, but not limited to:
 - a. Known family history of skeletal dysplasia.
 - b. Significant spinal abnormalities including but not limited to scoliosis, kyphosis and spina bifida variants.

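### Table 2-1 says children with impaired glucose tolerance are excluded, but no eligibility criterion excludes them

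*Protocol*

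**What the plan says.** Table 2-1 in Protocol Section 2.3.1 lists diabetes mellitus as a risk of growth hormone treatment. Its mitigation column calls for periodic glucose monitoring and then states a categorical exclusion: "Patients with pre-existing type 1 or type 2 diabetes mellitus or impaired glucose tolerance are excluded from participation in the study". The next sentence of the same cell reads "The doses of anti-hyperglycaemic medicinal products may require adjustment when GH therapy is instituted in these patients".

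The operative rule is criterion 5 in Section 5.2. It begins "Children diagnosed with diabetes mellitus or screening values from the central laboratory of" and gives two limits: "fasting plasma glucose above or equal to 126 mg/dL (7.0 mmol/L) or" and HbA1c of 6.5% or more. The key exclusion criteria in the synopsis (Section 1.1) repeat both limits.

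Criterion 10 in Section 5.2 is a general clause: "Any disorder, which in the investigator's opinion, might jeopardise participant's safety or compliance with the protocol".

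The opening of Section 5 adds: "Prospective approval of protocol deviations to recruitment and enrolment criteria, also known as protocol waivers or exemptions, is not permitted".

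**The concern.** The risk table and the eligibility rule disagree about who may enter the trial, and the disagreement concerns safety. The same row of Table 2-1 explains that growth hormone can lower insulin sensitivity, more so at higher doses and in susceptible patients, and that hyperglycaemia may follow where insulin secretion is inadequate. Every participant starts on 0.24 mg/kg/week, the highest of the three levels in the phase 2 dose-finding study (Section 4.3). Section 2.2.3.2 names diabetes among the diseases often associated with Turner syndrome, one of the four populations.

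Sites enrol from Section 5.2, while ethics committees and regulators weigh the risk from Section 2.3. The benefit-risk conclusion in Section 2.3.3 opens with "Taking into account the measures taken to minimise risk and burden to children participating in this study". One measure listed for that purpose is not secured by the criteria.

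**Working it through.** The plan gives no figure to reproduce. The check compares the text of the current protocol sections.

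**1. Conditions Table 2-1 says are excluded, against criterion 5**

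| Condition in Table 2-1 | Covered by criterion 5? |
|---|---|
| Type 1 diabetes | Yes, as diagnosed diabetes |
| Type 2 diabetes | Yes, as diagnosed diabetes |
| Impaired glucose tolerance | Not named |

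Two of the three are covered. The table lists impaired glucose tolerance separately from both types of diabetes, so a diabetes diagnosis cannot be read as including it.

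**2. The other exclusion criteria.** Section 5.2 has 13 general criteria and one for each indication (14 SGA, 15 TS, 16 NS, 17 ISS): 13 + 4 = 17. None names impaired glucose tolerance. Criteria 14 to 17 concern abnormalities that affect growth or its measurement.

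**3. Other places the rule could sit.** The inclusion criteria (Section 5.1), the synopsis exclusions (Section 1.1) and the country-specific requirements (Section 10.11) do not mention it.

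**4. Whether testing would catch it.** The glucose panel in Table 10-2 (Section 10.2) consists of fasting insulin, fasting plasma glucose, HbA1c and a calculated HOMA. It contains no glucose tolerance test. Only fasting plasma glucose and HbA1c carry exclusion limits.

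**5. The child who passes.** Known impaired glucose tolerance, no diabetes diagnosis, fasting plasma glucose below 126 mg/dL and HbA1c below 6.5%. Criterion 5 is not met, and exclusion then depends on criterion 10. Two sites could decide differently on the same child and both comply with Section 5.2.

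**6. Comparison within the same table.** The allergy row also states an exclusion. It refers the reader to Section 5.2, and criterion 1 there implements it. The diabetes row has no such reference, and one of its three conditions has no matching criterion.

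**7. The following sentence.** It speaks of adjusting anti-hyperglycaemic doses in patients whom the preceding sentence has just described as excluded. This is a drafting point, but it sits in the cell that needs editing.

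**The case against.** The strongest reply is that criterion 10 already does the work. Medical history and concomitant illness are recorded at screening (Sections 1.2 and 8.2), so known impaired glucose tolerance would be visible. Table 2-1 tells the investigator that it is a safety ground for exclusion. An investigator who reads both sections would be expected to use criterion 10. That lowers the practical risk, but it leaves to opinion what Table 2-1 states as fact. Because Section 5 does not permit waivers of enrolment criteria, the intended rule needs to be in the criteria.

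The second reply is that the residual risk is managed elsewhere. The glucose panel is repeated through the main and both extension periods (Sections 1.2 and 1.3). Investigators must review all laboratory results (Section 10.2), and abnormal values are listed (Section 9.3.5). Severe adverse events probably related to treatment can lead to dose reduction (Section 6.5.1), and an independent data monitoring committee reviews safety (Section 10.1.6.2). All of this is true and limits the weight of the point. Monitoring after enrolment is nevertheless a different safeguard from not enrolling.

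Third, Section 2.3.3 refers to risk-minimising measures in general and does not single this one out. That is fair: nothing shows that the benefit-risk conclusion would change without it.

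Finally, the documents do not show which of the two texts reflects the sponsor's intention, or whether enrolment is still open. That affects the choice of remedy; the two sections disagree in either case.

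**Conclusion.** The concern holds. Table 2-1 asserts an exclusion that Section 5.2 does not contain, and a site following Section 5.2 to the letter can enrol a child whom the risk section says is kept out.

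One of three stated conditions is left without a criterion. The children affected are those described in step 5 of the check, where criterion 10 is not applied. The documents give no count of them, so no proportion can be stated. No endpoint, estimand or analysis is affected, and the scheduled monitoring tempers the clinical consequence. The point is worth correcting because it concerns a safety ground for eligibility that the protocol itself puts forward. It rests only on reading the current text and assumes no outside definition of impaired glucose tolerance.

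**What to change.** - **If enrolment is open and the exclusion is intended:** add known impaired glucose tolerance, established by medical history, to criterion 5 in Section 5.2 and to the matching synopsis entry. Medical history is already collected, so no new test is needed.
- **If enrolment is closed, or the exclusion was not intended:** delete the reference to impaired glucose tolerance from the diabetes row of Table 2-1, and state that the mitigation is exclusion of diabetes under criterion 5 together with scheduled glucose monitoring.
- **In both cases:** correct the following Table 2-1 sentence so that it no longer describes dose adjustment for patients who are excluded. A cross-reference to Section 5.2, as in the allergy row, would help keep the two sections aligned.

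The cost is wording in one table cell, or in one criterion, its synopsis entry and that cell. No visit, test or analysis is added.

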2.3.2 Benefit assessment

Information gained from this study will support the development of a growth hormone product with clinical advantages over currently available products to children with SGA, TS, NS and ISS.

For most of the participating children the administration of study intervention during the study most likely reduces the treatment burden compared to current available therapy as somapacitan is administered once weekly.

It is expected that many participating treatment naïve children will experience increased height velocity compared to pre-study experience.

Participating children might benefit from the increased attention during the participation of the study which might lead to an increase in treatment adherence.

2.3.3 Overall benefit-risk conclusion

Overall, the safety profile of somapacitan is similar to the well-known safety profile of daily growth hormone products e.g., Norditropin® and no new safety concerns have been found during the conduct of the somapacitan study program.

There are well known risks associated with administration of injectable medication³⁶ as well as procedural risks as described in [Table 2-1](#). In this study the risks associated with administration of trial product as well as the risks associated with the study procedures are expected to be comparable to what is seen in routine clinical practice.

More detailed information about the known and expected benefits and risks and reasonably expected adverse events (AE) of somapacitan may be found in the IB.

Taking into account the measures taken to minimise risk and burden to children participating in this study, the potential risks identified in association with somapacitan are justified by the anticipated benefits that may be afforded to children with SGA, TS, NS and ISS.

3 Objectives, endpoints and estimands

Table 3-1 Objectives and endpoints

Objectives	Endpoints		
Primary	Title	Time frame	Unit

 To evaluate the safety of once-weekly somapacitan in children, either naïve or non-naïve to GH treatment, within each of the four indications: SGA, TS, NS or ISS. 		Primary endpoint: Number of adverse events (AEs) From baseline (week 0) to week 26 Number of AEs	
		Secondary supportive safety endpoint: Number of adverse events (AEs) possibly or probably related to somapacitan From baseline (week 0) to week 26 Number of AEs	
Secondary	Title	Time frame	Unit

 To evaluate the long-term safety of once-weekly somapacitan in children, either naïve or non-naïve to GH treatment, within each of the four indications: SGA, TS, NS or ISS. 		Secondary supportive safety endpoint: Number of adverse events (AEs) From baseline (week 0) to week 156 Number of AEs	

 To evaluate the efficacy of once-weekly somapacitan in children, either naïve or non-naïve to GH treatment, within each of the four indications: SGA, TS, NS or ISS. 		Secondary supportive efficacy endpoints: Height Velocity From baseline (week 0) to week 26 cm/year Change in Height SDS From baseline (week 0) to week 26 Score * Change in Height Velocity SDS From baseline (week 0) to week 26 Score * Change in IGF-1 SDS From baseline (week 0) to week 26 Score * Change in IGFBP-3 SDS From baseline (week 0) to week 26 Score *	

 To evaluate the steady state pharmacokinetics of once-weekly somapacitan in children, either naïve or non-naïve to GH treatment, within each of the four indications: SGA, TS, NS or ISS. 		Secondary supportive efficacy endpoint: Weekly average somapacitan concentration (C_{avg}) based on population PK analysis From baseline (week 0) to week 26 ng/ml	

*Positive score indicates that the value is closer to or above the reference population compared to baseline

Primary estimand

The primary clinical question of interest is: What is the incidence of AEs from baseline to week 26 in the four populations (SGA, TS, NS or ISS) in all patients while on treatment regardless of dose reduction?

For the primary objective, the same primary estimand is defined for each of the four populations (SGA, TS, NS or ISS) with 5 attributes:

- The treatment condition of interest is defined as somapacitan regardless of dose reduction
- The population targeted by the clinical question: The treatment effect will be assessed separately for each of the four populations (SGA, TS, NS or ISS)
- Endpoint: Number of adverse events from baseline to 26 weeks
- Remaining intercurrent events:
 - Treatment discontinuation for any reason: Participants data will be included up to 14 days after treatment discontinuation. Data collected 14 days after the intercurrent event will be regarded as not relevant for estimation of the treatment effect
 - Dose reduction due to IGF-I or AE: Is addressed by the treatment condition of interest attribute

There are no remaining intercurrent events

- Population-level summary: Event rate per 100 patient years

Rationale for estimand: The primary estimand assesses the expected safety profile in relation to incidence of AEs for a future population (SGA, TS, NS or ISS) while on somapacitan treatment for 26 weeks, if no treatment discontinuation occurs for any reason.

Secondary estimands

The supportive secondary safety estimand regarding the incidence of AEs possibly or probably related to somapacitan from baseline up to week 26 of somapacitan treatment will be evaluated in a similar way as the primary endpoint including possibly or probably related to somapacitan in the endpoint attribute.

The supportive secondary safety estimand regarding the incidence of AEs from baseline to week 156 of somapacitan treatment will be evaluated in a similar way as the primary endpoint substituting 156 weeks for 26 weeks.

The supportive secondary efficacy estimands will be specified in Section [9.3.3](#).

4 Study design

